5.0 Stratification Factors

- 5.1 Cancer stage: Residual (intact primary or metastatic) vs. no residual (no evidence of disease).
- 5.2 Risk: High risk vs. lower risk using validated Khorana score (see appendix III).

5.3 Location of initial thrombosis: deep-vein thrombosis (including atypical VTE) vs. pulmonary embolism.

6.0 Registration/Randomization Procedures

6.1 Registration Procedures

6.11 To register a patient, access the ACCRU web page at [REDACTED] click on “Training Page” and enter the registration/randomization application. The registration/randomization application is available 24 hours a day, 7 days a week. Back up and/or system support contact information is available on the Web site. If unable to access the Web site, call the Academic and Community Cancer Research United (ACCRU) Registration Office at [REDACTED] between the hours of 8 a.m. and 4:30 p.m. Central Time (Monday through Friday).

The instructions for the registration/randomization application are available by using the Help button. Prior to initiation of protocol study intervention, this process must be completed in its entirety and an ACCRU subject ID number must be available as noted in the instructions. It is the responsibility of the individual and institution registering the patient to confirm the process has been successfully completed prior to release of the study agent. Patient registration via the registration/randomization application can be confirmed in any of the following ways:

- Contact the ACCRU Registration Office [REDACTED] If the patient was fully registered, the ACCRU Registration Office staff can access the information from the centralized database and confirm the registration.
- Refer to “Instructions for Remote Registration” in section “Finding/Displaying Information about A Registered Subject.”

6.12 Documentation of IRB approval must be on file in the Registration Office before an investigator may register any patients.

In addition to submitting initial IRB approval documents, ongoing IRB approval documentation must be on file (no less than annually) at the Registration Office (fax: [REDACTED]). If the necessary documentation is not submitted in advance of attempting patient registration, the registration will not be accepted and the patient may not be enrolled in the protocol until the situation is resolved.

When the study has been permanently closed to patient enrollment, submission of annual IRB approvals to the Registration Office is no longer necessary.

6.13 Prior to accepting the registration/randomization, the registration/randomization application will verify the following:

- IRB approval at the registering institution
- Patient eligibility
- Existence of a signed consent form
- Existence of a signed authorization for use and disclosure of protected health information

- 6.14 Treatment cannot begin prior to registration and must begin ≤ 30 days after registration.
- 6.15 Pretreatment tests/procedures (see Section 4.0) must be completed within the guidelines specified on the test schedule.
- 6.16 Treatment on this protocol must commence at an ACCRU institution under the supervision of a health care professional.
- 6.17 Study drug is available on site.

6.2 Randomization Procedures

- 6.21 The factors defined in Section 5.0, together with the registering membership, will be used as stratification factors.
- 6.22 After the patient has been registered into the study, the values of the stratification factors will be recorded, and the patient will be assigned to one of the following treatment groups using the Pocock and Simon dynamic allocation procedure which balances the marginal distributions of the stratification factors between the treatment groups (Pocock-Simon).
 - Apixaban 2.5 mg twice daily.
 - Apixaban 5 mg twice daily.

6.3 Procedures for Double-Blinding the Treatment Assignment

- 6.31 After the treatment assignment has been ascertained by the registration/randomization application, the patient's study medication code number will be displayed on the confirmation of registration screen.
- 6.32 The data manager/nurse/pharmacist at the patient's institution must contact the ACCRU Registration Office for a code number when additional study product is needed for the patient.
- 6.33 ACCRU Registration Office personnel will monitor the supply of coded bottles at each participating institution and will arrange for the oncology pharmacist to send further supplies to the participating institutions as needed.

7.0 Protocol Treatment

7.1 Treatment Schedule

| Agent | Dose Level | Frequency | Route |
|----------|------------|--------------------------------------|-------|
| Apixaban | 2.5 mg | Twice daily for 12 months (365 days) | Oral |
| Apixaban | 5 mg | Twice for daily 12 months (365 days) | Oral |

*If a dose of apixaban is not taken at the scheduled time, the dose should be taken as soon as possible (+/-4 hours of the normal scheduled dose) on the same day and the prescribed dosing schedule should be resumed. If more than 4 hours late, then just wait for the next dose. The dose should not be doubled to make up for missed doses.

7.11 Scheduled visits every 30 days +/- 1 week (either in person or by scripted telephone interview with a study coordinator) should include a standardized assessment for recurrent thromboembolism, bleeding episodes, and adverse reactions. Patients should be instructed to report to the clinic immediately (or call 911/go to the Emergency Room) if they had any bleeding, or symptoms of recurrent deep-vein thrombosis, pulmonary embolism, or both. Written patient education materials will be provided to each patient outlining signs and symptoms to watch for regarding VTE recurrences (appendix VI). All suspected episodes of recurrent thrombosis should be investigated with the use of objective imaging.

7.2 Post protocol completion: Anticoagulation decision algorithm

7.21 Following the 12 months of protocol completion, a decision regarding anticoagulation continuation (off-study) will be clinically determined by the medical team caring for the patient. Although cancer is associated with a high risk of recurrent venous thromboembolism, the rate of recurrence differs significantly by cancer type, stage of disease, and stage progression over time (20). For the following patient characteristics, we recommend continuing anticoagulation: patients with brain, lung, pancreatic, or ovarian cancer; myeloproliferative or myelodysplastic disorders; stage IV cancer; cancer stage progression; or leg paresis. Anticoagulation options could include: continue apixaban (or other oral novel direct factor inhibitors), LMW heparin (dalteparin or enoxaparin), or warfarin.

For patients not meeting these specific criteria or if their presenting thrombus was limited to the calf (distal to and not including the popliteal vein), it is reasonable to discontinue anticoagulation therapy.

7.3 Breaking Codes in Double-Blinded Studies

The treatment code cannot be broken except in the event of an emergency for an individual patient. In the event of an emergency, call the ACCRU Registration Office at [REDACTED] to break the code on Monday through Friday, 8:00 a.m. to 4:30 p.m.

Central Time. Place a call to the ACCRU Registration Office and leave a message informing them of the need to un-blind a patient. Provide your contact information so that ACCRU Registration Office personnel can return the call the next business day. If a patient has been removed from the study and the clinician believes it is important to know what dose the patient was on, they can be unblinded. Before unblinding, all protocol data should be collected.

8.0 Dosage Modification Based on Adverse Events

8.1 Apixaban is cleared through several mechanisms including renal clearance, hepatic metabolism, and fecal excretion. Severe thrombocytopenia, liver and renal failure may increase bleeding risk. Patients with calculated creatinine clearance ≤ 30 ml/min (using the Cockcroft-Gault formula) must hold treatment until renal function improves to creatinine clearance >30 ml/min. They may get alternative anticoagulation treatment during this time period until renal function improves per the attending physician judgment.

For patients receiving either a strong CYP3A4 inducer or a strong CYP3A4 inhibitor (Appendix II), the medication should be discontinued or an alternative agent within the specific class of drug should be sought in order to participate in this study. If no good alternative agent within that class can be identified and the drug is required, the ACCRU Data Manager should be notified and the subject removed from the trial and go to observation.

For thrombocytopenia ($> 50,000/\text{microliter}$), no dose adjustment is necessary. For thrombocytopenia ($< 50,000/\text{microliter}$), apixaban will be held until platelet count recovers. Once the platelet count improves ($\geq 50,000/\text{microliter}$), the apixaban dose should be restarted.

If patients meet criteria for a major bleed, they will have met a major safety endpoint and will be removed from the study. The patient will then be managed, off-study, as appropriate per the clinical situation and current guidelines.

If patients meet criteria for a recurrent venous thromboembolic event, they will have met a major secondary endpoint and will be removed from the study. The patient will then be managed, off-study, as appropriate per the clinical situation and current guidelines.

If the patient suffers a non-major clinically relevant bleeding event, they will have met a major safety endpoint. Medical management will be provided in accordance with the location and severity of the bleeding event. This may include temporary cessation of study medication. Once the bleeding event has been appropriately managed, they can restart study medication, if considered clinically appropriate by the attending physician, and can be followed appropriately per protocol. They do not need to be removed from the study for this event.

8.2 Patients requiring any invasive procedure requiring temporary anticoagulant cessation will be managed as follows:

- (1) Date and type of procedure will be recorded on the CRF;
- (2) Apixaban will be discontinued at least 48 hours prior to elective surgery or invasive procedures with a moderate or high risk of bleeding, with no drug given on the procedure date; For low bleeding risk procedures, apixaban will be discontinued at least 24 hours prior to the procedure.
- (3) Post procedure, the patient should receive appropriate DVT prophylaxis per institutional guidelines. This could include prophylactic apixaban (open label dose of 2.5 mg twice daily) dosing for 48 hours; the first prophylactic dose will be given 24 hours after the procedure. Alternatively, low molecular weight heparin or unfractionated heparin would be reasonable.
- (4) Study drug will be withheld until 48 hours after the procedure and not initiated until adequate hemostasis is confirmed.

If apixaban treatment is temporarily held for any situation, the reason will be recorded on the CRF and the patient can go back on study for up to day 365 of the treatment schedule.

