3.0 Patient Eligibility

3.1 Inclusion Criteria

3.11 Age \geq 18 years.

3.12 Confirmed acute index (original venous thrombotic) event: lower extremity or upper extremity (jugular, innominate, subclavian, axillary, brachial) DVT, PE, splanchnic (hepatic, portal, splenic, mesenteric, renal, gonadal), or cerebral vein thrombosis for which the patient has received \geq 180 days (but \leq 365 days) of anticoagulant therapy prior to registration. The date, imaging modality, and location of index event will be required. The date of initiation and specific type of anticoagulants used will also be required.

3.13 Active cancer defined as metastatic disease and/or any evidence of cancer on cross-sectional or PET imaging, cancer related surgery, chemotherapy or radiation therapy within the past 6 months. Note: non-melanoma skin cancer does not meet the cancer requirement.

3.14 Life expectancy \geq 6 months.

3.15 ECOG Performance Status (PS) of 0, 1, or 2. (Form is available on the ACCRU web site
[REDACTED]

3.16 The following laboratory values obtained \leq 30 days prior to registration.

- Hemoglobin \geq 8 g/dL
- Platelet count \geq 50,000/mm³
- Alanine aminotransferase (ALT) or Aspartate transaminase (AST) \leq 3 x ULN
- Calculated creatinine clearance must be \geq 30 ml/min using the Cockcroft-Gault formula below:

Cockcroft-Gault Equation:

$$\text{Creatinine clearance for males} = \frac{(140 - \text{age})(\text{weight in kg})}{(72)(\text{serum creatinine in mg/dL})}$$

$$\text{Creatinine clearance for females} = \frac{(140 - \text{age})(\text{weight in kg})}{(72)(\text{serum creatinine in mg/dL})} * (0.85)$$

3.17 Negative serum or urine pregnancy test done \leq 7 days prior to registration, for women of childbearing potential only.
 Note: A woman of childbearing potential (WOCBP) is defined as any female who has experienced menarche and who has not undergone surgical sterilization (hysterectomy or bilateral oophorectomy) and is not postmenopausal. Menopause is defined as 12 months of amenorrhea in a woman over age 45 years in the absence of other biological or physiological causes.

3.18 Ability to provide informed written consent.

3.19 Willing to undergo monthly follow-up assessment, either in person at the enrolling institution or by telephone (script in Appendix V).

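### Sections 3.16 and 8.1 overlap at a creatinine clearance of exactly 30 ml/min, so a patient can be eligible and already under a mandatory temporary hold

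*Combined protocol and SAP*

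**What the plan says.** Two sections of the protocol set a creatinine clearance limit, both by the Cockcroft-Gault formula.

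- **Entry (section 3.16).** "Calculated creatinine clearance must be \geq 30 ml/min using the Cockcroft-Gault formula below". The value comes from baseline tests: "The following laboratory values obtained \leq 30 days prior to registration".
- **Hold (section 8.1).** "Patients with calculated creatinine clearance ≤ 30 ml/min (using the Cockcroft-Gault formula) must hold treatment". The hold lasts "until renal function improves to creatinine clearance >30 ml/min". Other anticoagulation may be given meanwhile, at the attending physician's judgment.

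Four other provisions bear on what follows for such a patient.

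- **Start of treatment (section 6.14).** "Treatment cannot begin prior to registration and must begin ≤ 30 days after registration".
- **Test schedule (section 4.0).** Creatinine is listed at baseline only.
- **Cancellation (section 13.3).** A patient removed before any study treatment is classed as a cancel.
- **Primary analysis (section 16.21).** The population is patients who took at least one dose of study drug.

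**The concern.** An eligibility limit and a hold limit on the same quantity should meet without overlapping. Here they share a point. A site with a patient at 30 ml/min finds that one section lets the patient be randomized and another withholds the drug from the outset. The protocol does not say whether the hold applies to the entry value, and sites could handle such patients differently.

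Two things are at stake. Section 8.1 gives bleeding risk as the reason for its rule, and bleeding is the primary endpoint, so the threshold should read the same way everywhere. In addition, a patient who is randomized but never released from the hold would be lost from the primary analysis through a drafting slip.

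**Working it through.** The plan states no figure for this group, so there is none to reproduce. The check compares the inequalities directly.

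**Step 1. Apply each rule around the boundary.**

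| Clearance (ml/min) | Eligible, 3.16 (30 or more) | Hold, 8.1 (30 or less) | Resumption allowed, 8.1 (above 30) | Result |
|---|---|---|---|---|
| 29.99 | No | Yes | No | Consistent |
| 30 | Yes | Yes | No | Eligible and held |
| 30.01 | Yes | No | Yes | Consistent |

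The overlap is the single value 30. The hold and resumption clauses agree with each other, so section 8.1 is consistent within itself. The mismatch lies between 8.1 and 3.16.

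**Step 2. Can the value occur?** Take the protocol's formula for males, with illustrative inputs of age 68, weight 60 kg and serum creatinine 2.0 mg/dL:

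(140 − 68) × 60 / (72 × 2.0) = 4,320 / 144 = 30.0 ml/min.

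So it can.

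**Step 3. How much depends on rounding?** Neither section says to what precision clearance is compared. As an illustration only, take an equal-weight grid: ages 40 to 90, whole-kilogram weights 45 to 120, creatinine 0.5 to 3.0 mg/dL in steps of 0.1, both sexes. These ranges are assumptions and do not represent a patient distribution.

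- Eligible combinations (30 or more, unrounded): 153,382.
- Exactly 30: 85, and 85 / 153,382 = 0.06%.
- Rounding to 30: 3,845, and 3,845 / 153,382 = 2.5% relative to the eligible count. Some of these lie just below 30 and are ineligible unless rounded.

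The ratio is 3,845 / 85, or about 45. The size of the affected group therefore turns almost wholly on an unstated rounding convention. The grid shows that sensitivity and does not forecast a number of patients.

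**Step 4. Follow the patient forward.** A patient registered at 30 is under the hold as worded. An unscheduled retest is not prohibited, but section 4.0 schedules none. If clearance rises above 30 within 30 days of registration, treatment can start in line with both 8.1 and 6.14. If it does not, the patient cannot start in line with both. A patient then removed undosed is a cancel under 13.3, and any patient never dosed is outside the population in 16.21.

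**Step 5. Effect on the design.** Section 16.1 raises the total from 352 to 370 for ineligibility and cancellation, a margin of 370 − 352 = 18 patients. Occasional losses at this boundary are of the kind that margin is meant to cover.

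**The case against.** The strongest reply is that section 8.0 concerns dose modification for adverse events, and that holding a drug until function improves suggests decline during treatment. On that reading 3.16 governs entry, 8.1 governs later events, and nothing conflicts. This is plausible but not conclusive. The renal sentence is not limited to new decline. The next paragraph of 8.1 deals with CYP3A4 drugs as a condition of taking part, and exclusion 3.24 refers to 8.1 for that purpose. The baseline creatinine is also the only one the protocol schedules. An immediate hold is thus what the words say, even if it may not be what was intended.

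Three stronger readings are tempting, and the documents do not support them.

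- **That sites are forced to break a rule.** They are not. Section 3.16 permits entry and does not order dosing. Registering the patient and holding the drug complies with both sections, and 6.14 leaves up to 30 days for a retest and start.
- **That such patients are barred from treatment.** The hold is temporary, alternative anticoagulation is allowed, and section 8.2 lets patients return after a temporary hold up to day 365.
- **That platelets show the same conflict.** Entry requires "Platelet count \geq 50,000/mm³", the hold applies only below 50,000, and at 50,000 or more "the apixaban dose should be restarted". A count of exactly 50,000 is eligible and is not held. The sentence on no dose adjustment leaves out that value, but no instruction conflicts.

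**Conclusion.** The inconsistency is real and minor. Sections 3.16 and 8.1 both include 30 ml/min by the same formula, and no provision says which prevails. A boundary patient can be randomized while under a mandatory temporary hold that no scheduled test can lift. If the hold outlasts the 30-day start window, the patient cannot be dosed in line with the protocol.

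The number affected is near zero if clearance is compared unrounded, and possibly a few if both sections work with whole numbers. The documents give neither a clearance distribution nor a rounding rule, so a reader should not infer a definite patient count. There is no material effect on power or type I error. The conclusion rests on reading 8.1 as worded, without limiting it to decline during treatment.

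**What to change.** Reconcile sections 3.16 and 8.1 so that no creatinine clearance value is both eligible and subject to a mandatory hold. The sponsor's clinical leads should choose the boundary; this review takes no position on it. In the same edit, state the precision to which clearance is compared, identically in both sections, and say whether 8.1 applies to the entry value.

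The cost is a changed inequality in one section and a sentence of clarification. Sample size, endpoints and analysis do not change. Depending on the boundary chosen, a very small number of patients at 30 ml/min may change eligibility status.

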4.0 Test Schedule

| Tests and procedures | ≤ 30 days prior to registration (baseline) | Every 30 days after the start of treatment (± 1 week) ³ | End of treatment |
|--|---|---|------------------|
| History and exam (including height and weight) | X | | |
| ECOG PS | X | X | |
| Adverse event assessment ³ | X | X | X |
| Hematology: 
 • CBC | X ¹ | | |
| Chemistry: 
 • SGOT (AST) or ALT • Creatinine | X ¹ | | |
| Selected concomitant meds ³ (see CRF for this form) | X | X | X |
| Pregnancy test ² | X | | |
| Patient education regarding signs and symptoms of thrombosis (Appendix VI) | X ⁵ | | |
| Patient Contact (including bleeding assessment, see App. IV and V) ³ | X | X | X |
| Patient compliance documentation ⁴ | | X | X |

1

1. ≤ 30 days prior to registration.
2. For women of childbearing potential only. Negative serum or urine pregnancy test done ≤ 7 days prior to registration.
3. If it is not feasible for the patient to return to the enrolling center for the monthly reassessment, a detailed history will be obtained by phone using a structured interview (see appendix V).
4. Use the questions in Appendix VII to obtain this information, and document the information on the appropriate case report form.
5. Prior to 1st study drug administration: Appendix VI given to patient and patient educated on signs/symptoms of potential thrombosis to monitor and report to study staff.

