10.0 Adverse Event (AE) Reporting and Monitoring

10.1 Adverse Event Characteristics

An Adverse Event [AE] is defined as any new untoward medical occurrence or worsening of a preexisting medical condition in a patient or clinical investigation subject administered an investigational (medicinal) product and that does not necessarily have a causal relationship with this treatment. An AE can therefore be any unfavorable and unintended sign (including an abnormal laboratory finding, for example), symptom, or disease temporally associated with the use of investigational product, whether or not considered related to the investigational product.

CTCAE term (AE description) and grade: The descriptions and grading scales found in the revised NCI Common Terminology Criteria for Adverse Events (CTCAE) version 4.0 will be utilized for AE reporting. All appropriate treatment areas should have access to a copy of the CTCAE version 4.0. A copy of the CTCAE version 4.0 can be downloaded from the CTEP web site:

10.11 Adverse event monitoring and reporting is a routine part of every clinical trial. First, identify and grade the severity of the event using the CTCAE version 4.0. Next, determine whether the event is expected or unexpected (see Section 10.2) and if the adverse event is related to the medical treatment or procedure (see Section 10.3). With this information, determine whether the event must be reported as an expedited report (see Section 10.4). **Important:** Expedited adverse event reporting requires submission of a Med Watch 3500A report(s). Expedited reports are to be completed within the timeframes and via the mechanisms specified in Sections 10.4. All AEs reported via expedited mechanisms must also be reported via the routine data reporting mechanisms defined by the protocol (see Sections 10.5 and 18.0).

10.12 Each CTCAE term in the current version is a unique representation of a specific event used for medical documentation and scientific analysis and is a single MedDRA Lowest Level Term (LLT).

- **NOTE:** A severe AE, as defined by the above grading scale, is **NOT** the same as serious AE which is defined in the table in Section 10.4.

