study period. The incidence curves of major bleeding and clinically relevant non-major bleeding will be plotted. The incidence of major bleeding and clinically relevant non-major bleeding will be summarized as a combined endpoint and separate endpoints by treatment arm. The difference in the incidences of the combined endpoint at 6 months and at 12 months between treatment arms will be estimated and tested using a normal approximation of the binomial distribution. All tests will be conducted at the one-sided 0.05 significance level.

The incidences of death due to cancer or other causes (without major bleeding or clinically relevant non-major bleeding) and adverse events that result in termination of treatment will be estimated and compared using the same approach.

A sensitivity analysis for these endpoints will be conducted using a stratified (by stratification factors listed in Section 5.0) Cox model adjusting for baseline covariates including location of DVT, renal clearance, age, sex, mobility at randomization, pulmonary disease, and cardiac disease.

16.22 Secondary Safety Analysis:

A secondary safety analysis of the primary safety endpoint will be performed on an intent-to-treat basis using the same approach described in Section 16.21. In addition, we will compare proportion of patients who experience at least one bleeding event (i.e. the primary endpoint) within 6 months of beginning treatment across the two study arms. As with the primary analysis, this will be done using a two-sample comparison of proportions with a one-sided alternative at a significance level of 5%.

16.23 Secondary Efficacy Analysis:

For the secondary efficacy analysis, the time to the first event of the composite DVT/PE outcome will be analyzed using the same method described in Section 16.21. For this outcome, death without DVT/PE and adverse events leading to termination of treatment will be treated as the competing risks.

16.3 Handling of Missing Data:

Monitoring and auditing procedures should be followed, in order to comply with Good Clinical Practice (GCP) guidelines. Each center will be audited at regular intervals to ensure compliance with the protocol, GCP and legal aspects. This will include on-site checking of the CRF for completeness and clarity, cross-checking with source documents, and clarification of administrative matters.

16.4 Interim Analysis and Study Monitoring:

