17.0 Pathology Considerations/Tissue Biospecimens – Not applicable

18.0 Records and Data Collection Procedures

18.1 Submission Timetable

NOTE: Access the RAVE system through the iMedidata portal at
 [REDACTED] All data must be entered by Remote Date Entry (RDE) and completed by qualified and authorized personnel. All data on the CRF must reflect the corresponding source document. Please refer to the ACCRU website for instructions
 [REDACTED]

Initial Material(s)

| CRF | Active-Monitoring Phase (Compliance with Test Schedule Section 4.0) |
|--|--|
| Institutional Contacts | |
| On Study | ≤2 weeks after registration |
| Laboratory Tests and Results: Baseline | |
| Patient Status: Baseline | |
| Concomitant Medications | |
| Off Treatment | Submit ≤1 week after registration if withdrawal/refusal occurs prior to beginning protocol therapy |

Test Schedule Material(s)

| CRF | Active Monitoring Phase (Compliance with Test Schedule Section 4.0) | |
|--|--|---------------------|
| | At each monthly evaluation during treatment | At end of treatment |
| Treatment (Intervention) | X | X |
| Treatment (Intervention): Dose Omissions | X | X |
| Recurrent Thromboembolism | X | X |
| Adverse Events: Solicited | X | X |
| Adverse Events: Other | X | X |
| Non-CTCAE Bleeding Grading | X | X |
| Concomitant Medications | X | X |
| Patient Status: Treatment | X | |
| Off Treatment | | X |
| ADR/AER | At each occurrence (see Section 10.0) | |
| Deviation | At each occurrence (see Section 10.0) | |

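### Section 8.1 requires holds for low creatinine clearance and low platelets, but no laboratory test is scheduled after baseline and the phone script asks for no result, so a site can follow the schedule and not learn that a hold applies.

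*Combined protocol and SAP*

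**What the plan says.** Section 8.1 sets two laboratory-based holds. At a Cockcroft-Gault clearance of 30 ml/min or below, patients "must hold treatment until renal function improves to creatinine clearance >30 ml/min". Below 50,000 platelets per microliter, "apixaban will be held until platelet count recovers", with restart at 50,000 or above. The section gives bleeding risk as the reason, and bleeding is the primary endpoint (Section 2.1).

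The parts of the plan that could supply these values after baseline are as follows.

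- **Test schedule (4.0).** CBC and creatinine are marked in the baseline column. The 30-day and end-of-treatment columns are blank for both.
- **Monthly contact (7.11).** "Scheduled visits every 30 days +/- 1 week (either in person or by scripted telephone interview with a study coordinator") must cover recurrent thromboembolism, bleeding and adverse reactions. Laboratory values are not listed. The footnote to Section 4.0 allows a phone substitute: "If it is not feasible for the patient to return to the enrolling center for the monthly reassessment, a detailed history will be obtained" by structured interview.
- **Phone script (Appendix V).** It asks about missed doses, clots, bleeding, procedures, activity level, weight, new medications and symptoms. It asks for no creatinine, platelet count or other laboratory result. Local records are sought only when there is evidence of bleeding or clotting.
- **Forms (18.1).** The one laboratory form listed is "Laboratory Tests and Results: Baseline". The on-treatment forms are named, but their content is not in the documents.

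**The concern.** Both holds are mandatory and both depend on a current laboratory value, yet the plan does not say how the site gets one once treatment has started. The background (Section 1.1) itself describes thrombocytopenia and renal failure as problems in this population, so crossing a limit during 12 months is foreseeable. Inclusion criterion 3.16 sets the entry floors at the same levels as the hold limits, so a patient can enter with no margin.

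What is at stake is exposure of individual patients. A hold works only if it comes before the next dose. If nobody asks for the value, the first sign that a hold was due may be the bleed itself, which is also the point at which Appendix V first sends the site for local records.

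**Working it through.** The plan states no figure to reproduce here. The check sets the rule against the schedule and then does simple arithmetic.

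**1. Required values after baseline.** Inputs: 365 treatment days (7.1), contacts every 30 days (4.0, 7.11).
- Contacts: 365 / 30 = 12.2, so 12 full intervals.
- Platelet or creatinine values required at those contacts or at end of treatment: 0.

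**2. Age of the only required values.** Inputs: laboratory tests up to 30 days before registration (3.16, 4.0), first dose up to 30 days after registration (6.14).
- Oldest at first dose: 30 + 30 = 60 days.
- At day 365: from 0 + 0 + 365 = 365 days to 30 + 30 + 365 = 425 days.

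**3. Margin between entry and hold.**

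| | Eligible (3.16) | Hold (8.1) | Margin |
|---|---|---|---|
| Platelets | at least 50,000 | below 50,000 | none |
| Clearance, ml/min | at least 30 | 30 or below | overlap at exactly 30 |

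Example of the overlap, with assumed values: a man aged 80, 72 kg, creatinine 2.0 mg/dL has (140 − 80) × 72 / (72 × 2.0) = 30.0. He is eligible and on hold at once.

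**4. How far creatinine must rise to reach the hold.** In the protocol's formula, at fixed age and sex, clearance is proportional to weight / creatinine. From baseline clearance C, the rise needed to reach 30 is C / 30 at constant weight and 0.9 × C / 30 after a 10% weight loss (an assumed figure).

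| Baseline clearance | Constant weight | 10% weight loss |
|---|---|---|
| 35 | 1.17-fold | 1.05-fold |
| 40 | 1.33-fold | 1.20-fold |
| 50 | 1.67-fold | 1.50-fold |
| 60 | 2.00-fold | 1.80-fold |

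Illustration, with assumed values: a woman aged 70, 60 kg, 1.0 mg/dL has 70 × 60 / 72 × 0.85 = 49.6 ml/min. At 54 kg and 1.5 mg/dL she has 70 × 54 / (72 × 1.5) × 0.85 = 29.75 ml/min and should be held. The phone script would pick up the weight change but not the creatinine.

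**5. Which situations the plan already covers.**
- *No test drawn.* The crossing cannot be detected.
- *Local test low, result not passed to the site.* No scheduled laboratory test and no question in the phone script brings it in.
- *Local test low and known to the site.* Section 8.1 obliges the site to hold, and the monthly adverse event assessment can capture the result. This case is covered.

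**The case against.** The best defence is that the plan has several routes by which an abnormal result can reach Section 8.1. An adverse event includes "any unfavorable and unintended sign (including an abnormal laboratory finding, for example"). Adverse events are assessed every 30 days (4.0) and graded at each evaluation (10.51). Section 10.318 extends recording to worsening found in procedures that the protocol does not require, and 10.522 requires submission of grade 3 and 4 events whatever their attribution. The reason for any hold goes on the CRF (8.2). A deviation form exists ("Deviation | At each occurrence (see Section 10.0"), and audits under Section 16.3 include "on-site checking of the CRF for completeness and clarity, cross-checking with source documents". Many of these patients may also have routine oncology blood tests.

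Much of this stands. The adverse event route is monthly and is not merely retrospective. A reader might infer that the plan lets a site keep dosing on a known low value, or that a missed hold could never come to light. The documents support neither inference: dosing on a known qualifying value would breach 8.1, and it could be found through adverse event reporting, the deviation form or audit.

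What remains is that none of these routes orders a test or, as far as the documents show, asks for a local result. Deviation forms and audits also act after the dose was taken. Nor do the documents show that every patient has regular local tests: active cancer can rest on surgery in the past 6 months (3.13), patients with no evidence of disease form a stratum (5.1), and hospice patients may stay on study drug (13.7).

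One caveat cannot be resolved. The monthly solicited adverse event and patient status forms might contain a platelet or creatinine item. A form item would help with results that exist but would still not order a test.

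**Conclusion.** The gap is real and limited to detection. Section 8.1 makes two bleeding-safety holds mandatory, while the schedule, the phone script and the named forms require no platelet count or creatinine after baseline: 0 required values over 12 contacts, with the last required value 365 to 425 days old at day 365. A site can complete every scheduled procedure and not learn that a hold applies. The double status of a clearance of exactly 30 is a separate, small wording mismatch, which 8.1 already resolves on the cautious side.

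The conclusion rests on the documents as shown, with the content of the monthly forms unknown. The fold-rises and patient examples are illustrations, not estimates. The documents give no baseline distribution of clearance or platelets and no crossing rate, so the number of missed holds cannot be derived. A reader might also infer that missed holds bias the comparison of the two doses or weaken its power. Nothing in the documents shows that they would differ between blinded arms, and no such effect is claimed. The point is patient safety, and the change is cheap enough that it should be made.

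**What to change.** 1. State in Section 8.1 that the holds act on local laboratory results.
2. Before the first dose and at each existing 30-day contact, in person or by phone, obtain and record the date and value of the latest local platelet count and creatinine. Recalculate Cockcroft-Gault clearance with current weight and apply the 8.1 holds.
3. Flag to the treating physician any patient with no result within a stated window, for example 60 days. Whether to order a test stays a clinical decision.
4. Align the boundary between 3.16 and 8.1, for example hold below 30 and restart at 30 or above.

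The document changes are a row in the Section 4.0 schedule, one or two lines in Appendix V, a short CRF page, and small edits to 3.16 and 8.1. No study blood draw is required, which fits Section 19.2 (no research-funded tests). For the same reason a fixed recheck interval during a hold is left out: it would imply draws at set times.

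The downsides are a small workload at 12 contacts per patient plus one look-up before dosing, record retrieval that depends on patient consent, and values that may be weeks old. Patients with no local tests are flagged but not otherwise covered unless the physician orders one.
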